#### **2.1.4.8 Holter Monitoring**

Holter ECG will be collected on Visit 3 (Week -1), on Visit 10 (Week 14), and on Visit 12 (Week 26, primary endpoint assessment visit). The Holter monitor will be proposed to first up to 50% of patient who agree. Twenty-four hour average and night time average heart rate will be derived based on the holter monitoring. Twenty-four hour interval is defined to be from the time of dosing until 24 hours post dose. Night time is defined to be the interval from 12 hours post dose until 24 hours post dose. For Visit 3, time of dosing is expected time of dosing on Day 1.

#### **2.1.4.9 Anti-SAR425899 antibody assessment**

Anti-SAR425899 antibody status (Positive, Negative), antibody levels (titer or concentration) will be collected on the safety population and only in patients from SAR treatment groups.

The TEAE period for antibody variables is defined in [Section 2.1.4](#).

### 2.1.5 Pharmacokinetic variables

Pharmacokinetics variables include plasma concentrations of patients in the SAR425899 groups.

### 2.1.6 Pharmacodynamic biomarkers, NASH and cardiovascular biomarkers

Pharmacodynamic biomarkers are:

- Change waist circumference, hip circumference, waist to hip ratio from baseline to Week 26,
- Change in visual analogue scale (VAS) for appetite/satiety score in response to a standardized meal test in up to 50% subset of all patients from baseline to Week 26 at time points premeal, 4 hours post meal,
- Change in fasting level of adiponectin from baseline to Week 26.

Waist circumference, hip circumference, waist to hip ratio are assessed at Visit 4 (Day 1) before first IP injection; at Visit 10 (Week 14); and at final assessment (Visit 12 at Week 26, primary endpoint assessment visit).

VAS for appetite/satiety score will be measured at premeal and 4 hours post meal at Visit 3 (Week -1); and at final assessment (Visit 12 at Week 26, primary endpoint assessment visit) in up to 50% subset of all patients

Fasting level of adiponectin will be assessed at Visit 4 (Day 1) before first IP injection; at Visit 10 (Week 14); and at final assessment (Visit 12 at Week 26, primary endpoint assessment visit).

### 2.1.7 NASH and cardiovascular biomarkers

- Change in NASH biomarkers from baseline to Week 26:  $\alpha$ 2-macroglobulin, apolipoprotein A1, haptoglobin, CK18, GGT, ALT and AST.
- Change in Cardiovascular biomarkers from baseline to Week 26: high-sensitivity C-reactive protein (hs-CRP), brain natriuretic peptide (BNP).

### 2.1.8 Patient reported outcomes

The patient-reported outcome (PRO) questionnaires in this study are the Weight-Related Symptoms Measure (WRSM), the Ability to Perform Physical Activities of Daily Living (APPADL, initially called the Impact of Weight on Activities of Daily Living) and the Impact of Weight on self-perception (IW-SP). The questionnaires are attached in the [Appendix E](#).

The 3 PRO questionnaires will be administered at baseline and Week 26. The patients will be requested to complete the questionnaires by themselves during selected clinical visits in specific booklets, independently from investigator, site staff and any help from friends or relatives. For validity purposes, patients will be asked to answer all the questions of the questionnaires at the start of the visit in a quiet place, before any procedures/tests and before discussing with the investigator, and while on site to return the completed questionnaires to the investigator or his/her designee on the same day.

In case of early IMP discontinuation, the questionnaires will be administered at the visit planned for the last dosing day with IMP and afterwards as normally planned.

The WRSM is a validated PRO questionnaire to measure the presence and bothersomeness of obesity symptoms (1). It was developed with and for obese and overweight adults. It includes 20 items on shortness of breath, tiredness, sleep problems, sensitivity to cold, increased thirst, increased irritability, back pain, frequent urination, pain in the joints, water retention, foot problems, sensitivity to heat, snoring, increased appetite, leakage of urine, lightheadedness, increased sweating, loss of sexual desire, decreased physical stamina, and skin irritation. The presence of each symptom is first asked to patient (Yes/No) and then the bothersomeness of symptom is evaluated on a 7-point Likert scale (from 0 [not at all] to 6 [a very great deal bothersomeness]). A total score is calculated by summing the bothersomeness for each symptom, ranging from 0 to 120, with lower scores corresponding to less bothersomeness. The completion time of the WRSM is less than 5 minutes. It demonstrated robust psychometric properties in obese and overweight people including its responsiveness to weight decrease.

#### **APPADL:**

The APPADL, previously named the Impact of Weight on Activities of Daily Living (IW-ADL) is a validated PRO questionnaire to measure the ability of moderately obese individuals with T2DM to perform daily physical activities (2). It was developed with T2DM individuals with BMI between 25 and 40 kg/m^2. It includes 7 items on flexibility, mobility, and activity level, evaluated on a 5-point Likert scale (from 1 [unable to do] to 5 [not at all difficult]). A total score is calculated by summing the 7 items and dividing by the number of items, it ranges from 1 to 5, with higher scores corresponding to greater ability to do physical daily activities. The completion time of the APPADL is estimated to be less than 5 minutes. It demonstrated robust psychometric properties in patients with T2DM and BMI >30 kg/m^2 and was able to discriminate patients who achieved at least 5% weight loss from others who did not (3).

A raw total APPADL score is calculated by summing the 7 item scores and dividing by the number of items (7). The raw APPADL total score ranges from 1 to 5. To transform the APPADL total score to a scale ranging from 0 to 100, the following transformation formula is used:

$$\frac{[(\text{actual raw score} - \text{lowest possible score}) / \text{raw score range} (\text{highest possible score} - \text{lowest possible score})] \times 100}{}$$

For example, using the transformation formula, a raw APPADL total score of “3.0” becomes a transformed total score of “50.0” on a scale of 0 to 100:

$$[(3.0-1.0)/(5-1)] * 100 = 2/4 * 100 = 50.0$$

Higher raw APPADL raw total scores and higher transformed APPADL total scores correspond to better self-reported ability to perform physical activities of daily living.

Missing data imputation for APPADL can be found in [Section 2.5.9](#).

## **IW-SP:**

The IW-SP is a validated questionnaire to assess an individual's self-perception related to his or her weight. It was developed with moderately obese individuals with T2DM (BMI 25 to 40 kg/m^2) (4). It includes 3 items on unhappiness with appearance, self-consciousness in social situations, and overall self-perception, evaluated on a 5-point Likert scale (from 1 [always] to 5 [never]). A total score is calculated by summing the 3 items and dividing by the number of items, it ranges from 1 to 5, with higher scores corresponding to better self-perception. The completion time of the IW-SP is estimated to be less than 2 minutes. It demonstrated robust psychometric properties in patients with T2DM and BMI >30 kg/m^2 and was able to discriminate patients who achieved at least 5% weight loss from others who did not.

A raw total IW-SP score is calculated by summing the 3 item scores and dividing by the number of items (3). The raw IW-SP total score ranges from 1 to 5. To transform the IW-SP total score to a scale ranging from 0 to 100, the same transformation formula as APPADL is used. For example, using the formula, a raw IW-SP total score of "2.0" becomes a transformed total score of "25.0" on a scale of 0 to 100:

$$[(2.0-1.0)/5-1] * 100 = 1/4 * 100 = 25.0$$

Higher raw IW-SP total scores and higher transformed IW-SP total scores correspond to better self-perception.

Missing data imputation for IW-SP can be found in [Section 2.5.9](#).

## **Patient qualitative assessment of the treatment**

In addition of the 3 PRO questionnaires, patients will be asked to answer questions at the end of the treatment period (Week 26). This patient qualitative assessment of treatment aims to better understand patients' views on benefits and disadvantages of the treatment they experienced during the trial. The two first questions will ask patients to describe in free text the benefits and disadvantages of the drug they experienced during the trial. A third question will ask patients if they would be willing to pursue the treatment they had during the trial (yes/no) and to describe the reasons in free text. Finally, patients will be asked to give their perception of the drug benefit-risk on 7-point Likert scale ranging from -3 (disadvantages significantly outweigh the benefits) to 3 (Benefits significantly outweigh the disadvantages) and where 0 corresponds to 'Equal benefits and disadvantages'. This patient qualitative assessment should take between 10 and 20 minutes. Patients' answers to the 3 first questions will be analyzed qualitatively. Due to the availability of this questionnaire only in English, it will be limited to English speakers in United States and Canada only.

## 2.2 DISPOSITION OF PATIENTS

This section describes patient disposition for both patient study status and the patient analysis populations.

Screened patients are defined as all patients who have signed the informed consent.

Randomized patients consist of all patients who have signed informed consent, with a treatment kit number allocated and recorded in the interactive response technology (IRT) database, regardless of whether the treatment kit was actually used or not.

For patient study status, the total number of patients in each of the following categories will be presented in the clinical study report (CSR), using a flowchart diagram or summary table:

- Screened patients
- Screen failure patients and reasons for screen failure
- Nonrandomized but treated patients
- Randomized patients
- Randomized but not treated patients
- Randomized and treated patients
- Patients included in each of the substudy (meal test and holter monitor)
- Patients who have completed the 26-week treatment period as per protocol
- Patients who permanently discontinued the IMP, the main reason for treatment discontinuation, and subject's request for treatment discontinuation
- Patients who complete the study as per protocol
- Patients who did not complete the study as per protocol and the reasons for study discontinuation
- Patients' end of study status (completed, not completed) by end of treatment status (completed, not completed)
- Status at last study contact.

For the screened, screen failure, and non-randomized but treated patients, percentages will be calculated using the number of screened patients as the denominator. All other categories of patients will be presented by treatment group, and percentages will be calculated using the number of randomized patients within each treatment group as the denominator. Reason for treatment/study discontinuation will be provided in tables giving numbers and percentages by treatment group.

A summary of the distribution of patients by country and center will also be provided (overall number of patients screened, screened but not randomized, randomized, and randomized but not treated, and number of patients randomized and discontinued from study treatment for each treatment group).

Patients treated but not randomized, randomized but not treated, patients randomized but not treated as randomized will be identified and described in separate listings. Patients of the second category (randomized and not treated) will be part of efficacy analyses. Patients of the third

category (randomized and not treated as randomized) will be part of efficacy and safety analyses (see [Section 2.3](#)). Safety data of patients treated but not randomized will be reported separately.

The randomization strata [HbA1c at screening ( $<8\%$ ,  $\geq 8\%$ ) and Visit 4 (Day 1) BMI ( $<35.0 \text{ kg/m}^2$ ,  $\geq 35.0 \text{ kg/m}^2$ )] assigned by IRT will be summarized. The percentages will be calculated using the number of randomized patients as the denominator. The discrepancy between the strata assigned by IRT and the information reported on eCRF will be listed for all randomized patients.

Kaplan-Meier (KM) plots of the cumulative incidence of IMP discontinuation due to any reason or due to AE will be provided for the 26-week treatment period. Additionally, a listing of these patients, along with the reason for treatment discontinuation, study completion status and the reason for study discontinuation, will be provided. Time to treatment discontinuation will be defined as the number of days from the first injection of IMP until the day of treatment discontinuation. All completers will be considered as censored observations. The censoring time will be the number of days from the first injection of IMP until the last injection date during 26-week treatment period.

All major or critical deviations including deviations related to randomization procedure will be listed and summarized in tables giving numbers and percentages of deviations by randomized treatment group.

Additionally, the analysis populations for efficacy, safety, PK, and each of the substudy defined in [Section 2.3](#) will be summarized in a table by number of patients on the randomized population:

- Efficacy population: modified intent-to-treat (ITT) population,
- Safety population.
- PK population.
- Substudies

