10.3.2 Permanent treatment discontinuation with investigational medicinal product(s)

Permanent treatment discontinuation is any treatment discontinuation associated with the definitive decision from the Investigator or the patient not to re-expose the patient to the IMP at any time.

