10.3.3 List of criteria for permanent treatment discontinuation

The patients may withdraw from treatment with the IMP if they decide to do so, at any time and irrespective of the reason, or this may be the Investigator's decision. All efforts should be made to document the reason(s) for treatment discontinuation and this should be documented in the eCRF.

Patients may withdraw from treatment with IMP in case of the following reasons:

- At patient's own request, ie, withdraw of consent for treatment.
- If, in the investigator's opinion, continuation with the administration of IMP would be detrimental to the patient's well-being.
- At the specific request of the sponsor.

A patient must withdraw from treatment with IMP in case of the following:

- Intercurrent condition that requires discontinuation of IMP: eg, laboratory abnormalities (see decision tree and general guidance for the follow up of laboratory abnormalities in [Appendix C](#)), diagnosis of acute pancreatitis confirmed by gastroenterologic evaluation and imaging (see [Section 10.6.4](#)), calcitonin value ≥ 50 pg/ml (see [Section 10.6.6](#)).
- Pregnancy.
- Systemic hypersensitivity reaction.

Any code-breaking requested by the Investigator will lead to permanent treatment discontinuation.

Any abnormal laboratory value or ECG parameter will be immediately rechecked for confirmation (eg after 24 hours) before making a decision of permanent discontinuation of the IMP for the concerned patient.

Handling of patients after permanent treatment discontinuation

Patients will be followed-up according to the study procedures specified in this protocol up to the scheduled date of study completion, or up to recovery or stabilization of any AE to be followed-up as specified in this protocol, whichever comes last.

If possible, and after the permanent discontinuation of treatment, the patients will be assessed using the procedure normally planned for the last dosing day with the IMP including a pharmacokinetics sample if already scheduled.

All cases of permanent treatment discontinuation should be recorded by the Investigator in the appropriate pages of the eCRF when considered as confirmed.

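### The Kaplan-Meier plot of IMP discontinuation due to AE is labelled a cumulative incidence, but stops for other reasons compete with AE stops and their handling is not stated

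*SAP*

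**What the plan says.** SAP section 2.2 (Disposition of patients) uses one estimator for two endpoints: "Kaplan-Meier (KM) plots of the cumulative incidence of IMP discontinuation due to any reason or due to AE will be provided". The event time is set out as follows: "Time to treatment discontinuation will be defined as the number of days from the first injection of IMP until the day of treatment discontinuation". One group is named as censored: "All completers will be considered as censored observations". The censoring rule reads: "The censoring time will be the number of days from the first injection of IMP until the last injection date during 26-week treatment period". Nothing in the section says what happens, in the AE curve, to a patient who stops the IMP for a reason other than an AE. Neither document names a competing-risk estimator.

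The protocol provides for such stops. Section 10.3.3 includes "At patient's own request, ie, withdraw of consent for treatment", a request by the sponsor, and code-breaking: "Any code-breaking requested by the Investigator will lead to permanent treatment discontinuation". Section 10.3.2 makes a permanent stop final, because it is a decision "not to re-expose the patient to the IMP at any time".

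The SAP also plans the crude figures. In section 2.2: "Reason for treatment/study discontinuation will be provided in tables giving numbers and percentages by treatment group". Section 2.4.5.2 adds AE-based counts of treatment discontinuation, in the TEAE overview and in a table by system organ class and preferred term.

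**The concern.** For discontinuation due to any reason, 1-KM is a proper cumulative incidence, because no other cause of stopping competes with the event. Discontinuation due to AE is different. A patient who has permanently stopped for another reason can no longer stop for an AE. Censoring that patient treats the AE stop as still possible and estimates what would happen if other stops did not occur. That is not the quantity named in the label.

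Safety is a main secondary objective of this dose-ranging trial, and readers will look at these curves to judge tolerability by dose. If the curve sits above the share of patients who actually stopped for an AE, and by an amount that can vary with each arm's other stops, it answers a question other than the one its label suggests.

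**Working it through.** **Inputs.** The documents give no discontinuation rate and no figure for this plot, so there is no plan figure to reproduce. The 26-week period and the 60 patients per SAR425899 arm come from the documents. All stop rates below are assumptions.

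**Check 1: constant hazards over 26 weeks.** Let a be the true cumulative incidence of AE stops at Week 26 and b that of other stops.

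- Total cumulative hazard: H = -ln(1 - a - b).
- AE share of it: H × a/(a + b).
- Kaplan-Meier with other stops censored: 1-KM = 1 - exp(-H × a/(a + b)).

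Example with a = 15%, b = 10%: H = -ln(0.75) = 0.2877. The AE share is 0.2877 × 0.6 = 0.1726. So 1-KM = 1 - exp(-0.1726) = 15.9%, against a true 15%.

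1-KM at Week 26 for other assumed rates:

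| True AE incidence | other 5% | other 10% | other 20% | other 30% |
|---|---|---|---|---|
| 10% | 10.3% | 10.6% | 11.2% | 12.0% |
| 15% | 15.4% | 15.9% | 16.9% | 18.1% |
| 20% | 20.6% | 21.2% | 22.5% | 24.2% |
| 30% | 30.9% | 31.8% | 34.0% | 36.8% |

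For AE stops of 10-20% and other stops of 5-20%, the gap runs from 0.27 points (10% with 5%) to 2.54 points (20% with 20%). With no other stops the two quantities agree.

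**Check 2: timing, without a hazard assumption.** Take one arm of 60 with 9 AE stops, so the crude incidence is 9/60 = 15.0%. The two extreme orderings give:

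- All AE stops first: 1-KM = 9/60 = 15.0%, whatever the number of later stops.
- All other stops first: the risk set has shrunk before the first AE stop, so 1-KM = 9/(60 - other stops). With 3, 6, 12 or 18 other stops this is 9/57 = 15.8%, 9/54 = 16.7%, 9/48 = 18.8% or 9/42 = 21.4%.

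The overstatement is never negative, and its size depends on order as well as number.

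**Check 3: the alternative reading.** If non-AE stoppers were kept in the risk set to Day 182 and not censored at their stop, the product-limit curve would match the cumulative incidence. The SAP wording does not exclude this, but the only censoring time it gives is the last injection. Applied to a non-AE stopper, that removes the patient at the stop.

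**The case against.** The strongest reply is that the defect is inferred. The SAP names completers as censored and is silent on non-AE stoppers, so a reader who concludes that the curve will certainly overstate AE discontinuation goes further than the text. This stands: censoring at the stop is the usual Kaplan-Meier convention and the likelier reading, but it is not written.

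A reader might also infer that the comparison between arms will be distorted, for example by placebo patients stopping for lack of efficacy. The documents do not support that. Under protocol section 8.8.2 inadequate control leads to rescue therapy with study treatment continued. Section 10.3.3 does not list lack of efficacy as a reason to stop, and section 8.3.1 withholds post-baseline HbA1c and FPG from the investigator apart from threshold alerts. The gap can differ between arms, but nothing indicates in which direction.

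The size is also open to challenge. Dose increases fall in the first three weeks, and a further attempt after intolerance must come before Week 8, so AE stops may cluster early and the gap may be close to nil. At moderate rates the gap is small beside sampling error: the binomial standard error of a 15% rate is √(0.15 × 0.85/60) = 4.6 points with 60 patients and √(0.15 × 0.85/30) = 6.5 points with the 30 pooled placebo patients. This stands as a limit on importance. It does not make the estimator match its label, since the gap has a fixed sign.

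A mismatch between the curve and the disposition table would not by itself prove the error. The curve runs from first injection while the table divides by randomized patients, and the Aalen-Johansen estimator would not remove that difference.

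Finally, a cumulative incidence also depends on other stops: with equal AE hazards, the arm with more of them shows fewer AE stops. Neither display isolates tolerability. That is true, but the cumulative incidence is the quantity the SAP says it will plot.

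**Conclusion.** The point holds as a minor one. SAP 2.2 pairs a Kaplan-Meier estimator with a cumulative-incidence label for AE discontinuation and leaves the handling of other stops unstated. On the ordinary reading, 1-KM equals or exceeds the true cumulative incidence. The excess is about 0.3 to 2.5 points for AE stops of 10-20% with other stops of 5-20%. That range rests on assumed rates and constant hazards, and the excess is near zero if AE stops come before other stops.

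The plot is descriptive, no test depends on it, and the crude proportions are already planned, so no conclusion of the trial turns on it. The any-reason curve needs no change.

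**What to change.** In SAP 2.2, state that discontinuation due to AE will be plotted by treatment group with the Aalen-Johansen cumulative incidence function, treating discontinuation for any other reason as a competing event and censoring completers at their last injection. Keep Kaplan-Meier for discontinuation due to any reason.

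If all treated patients either stop or complete by Week 26, the Week 26 value of the AE curve then equals the crude AE proportion among treated patients.

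The cost is one sentence and a small programming change. No new data are needed, since the reason and date of discontinuation are already collected. If the sponsor prefers to keep Kaplan-Meier for the AE curve, the minimum is to write down the censoring rule and label the plot as a Kaplan-Meier estimate censored at other stops.
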